We propose that cocaine-induced reductions in sweating and skin blood flow will result in excessive elevations in core temperature during exercise in warm environmental conditions. Thus, the objective of this work is to test the hypothesis that intranasal cocaine impairs core temperature responses during mild to moderate intensity exercise while in warm environmental conditions.

b. Current practice

A cocaine solution, administered in each nostril to achieve analgesia and vasoconstriction, is commonly used in rhino-surgical procedures (PMID: 32730351, 16848922, and 26452438). According to the product insert, "The total dose for any one procedure or surgery should not exceed 3 mg/kg cocaine hydrochloride", which is the basis for our decision to not administer more than 3 mg/kg cocaine for any one procedure.

Form A

[figure not shown]
[figure not shown]
STU-2023-0094

A lidocaine solution is also commonly used for related procedures (PMID: 26452438, 24980226, and 30017430) at doses similar to proposed with the present protocol.

3. Study Design.

Describe the study design (e.g., single/double blind, parallel, crossover, etc.) Consider inserting a scheme to visually present the study design.

We will conduct a double-blind, placebo-controlled, crossover study. Following informed consent and screening, eligible participants will be randomized to complete the cocaine or the placebo (lidocaine) trial first, with the other “agent” administered during the subsequent visit. After the administration of either of these drugs, the participant will perform mild to moderate intensity exercise in warm environmental conditions (no higher than 41 °C).

**EXPERIMENTAL PROTOCOL****4. Research Plan / Description of the Research Methods:****4.a. Provide a comprehensive narrative describing the research methods.**

- 1) Provide the **order in which tests/procedures will be performed**,
- 2) Provide the **setting** for these events and a description of the **methods used to protect privacy** during the study.
- 3) Provide the **plan for data analysis** (include as applicable the **sample size calculation**)

Please respond to all components of this item, or clearly indicate which components are not applicable.

Inclusion:

- 18-50 years of age
- Healthy
- Non-obese (body mass index less than 31 kg/m²)
- Speak English
- Systolic blood pressure <140 mmHg
- Diastolic blood pressure <90 mmHg

Exclusion:

- Subjects not in the defined age range

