The setting for all visits will be the Institute for Exercise and Environmental Medicine. Trials will be conducted in controlled laboratory settings. A physician with a license to prescribe schedule II drugs ([name] DO, [name] MD, or [name] MD), or a research nurse (with oversight from that physician) will administer cocaine (no higher than 3 mg/kg body mass) or placebo (lidocaine, no higher than 3 mg/kg body mass) during each experimental visit. We will assess core and skin temperatures, local and whole-body sweat rate, brachial blood pressure, heart rate via electrocardiogram, respiration rate (from metabolic cart), compensatory reserve via photoplethysmography, and plasma catecholamine concentrations from blood samples collected prior to and after exercise (~3 tablespoons per experimental visit). In addition, ratings of perceived exertion and thermal perception will be obtained.

Data analysis will be performed as done previously in [name] laboratory in companion studies addressing the same questions but during passive heating rather than exercise (PMID: 12044126). Specifically, we will compare thermoregulatory and cardiovascular data (e.g., baseline and end-exercise)

between placebo and cocaine trials. All data will be analyzed while blind to condition and with proper covariate analyses.

Personal health information (PHI) that is collected will be kept in a key-lock filing cabinet in a key-lock room only accessible to study team members within a numeric-padlocked laboratory. As described in the eIRB portal, a coded number system will be used in place of the participants name to de-identify their research information collected. A participant ID key, only accessible to study team members, will link the participants 'information with the coded number. Additionally, we follow all applicable University of Texas Southwestern IRB and Institute of Exercise and Environmental Medicine (i.e., where the research will take place) guidelines for protecting research participant privacy.

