Up to 30 participants are anticipated to enroll in this study, with a goal of obtaining complete datasets on 20 individuals. No study has evaluated the effects of cocaine on core temperature responses during exercise in warm (or thermoneutral) environmental conditions. The power and sample size estimates are based on findings from [name] laboratory investigating core temperature responses to 60 min of exercise in burn survivors. Our rationale for using burn survivors is the expectation that the suppression in sweating in burn survivors with 20-40% body surface area burn may be similar to the suppression in sweating caused by cocaine. The power analysis was calculated using G*Power [Ttests – Means: Difference between two dependent means (matched pairs)] using a projected ~25% heightened increase in core body temperature following 60 minutes of exercise with cocaine relative to when participants received placebo (i.e., placebo: 0.82 ± 0.36 °C, cocaine: 1.02 ± 0.40 °C). These predictions resulted in an effect size of 0.60. With a study power=0.81 at an alpha=0.05, yielded an estimated subject size of 19 individuals. That value was inflated to 20 subjects (10 male and 10 female) to permit an exploratory comparison in the primary responses between sexes. Given the potential for subject dropouts, we propose to recruit up to 30 individuals to obtain complete datasets from 20 subjects. Since the effects of cocaine on thermoregulatory responses during exercise have never been assessed, the indicated values are estimates and thus interim power analyses will be performed, with the number of required subjects adjusted based upon the variance of the obtained data.

4.b. List of the study intervention(s) being tested or evaluated under this protocol

	N/A - this study does not test or evaluate an intervention. Skip to item 4.d.		
#	Study intervention(s) being tested or evaluated under the protocol Add or delete rows as needed	Affiliate Place a check next to institution(s) where the intervention will be performed	Local Standard Practice? Indicate whether the intervention is considered acceptable practice locally for applicable institutions

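### The stated power of 0.81 with 19 participants holds only for a one-sided test that the plan never declares; two-sided at 0.05 it is 0.70, or 0.72 with 20 completers

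*Combined protocol and SAP*

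**What the plan says.** The sample size paragraph of section 4.a (Combined protocol and SAP) names the G*Power procedure for "Difference between two dependent means (matched pairs") and projects the rise in core temperature over 60 minutes of exercise as "placebo: 0.82 ± 0.36 °C, cocaine: 1.02 ± 0.40 °C". It continues: "These predictions resulted in an effect size of 0.60". The result is then given: "With a study power=0.81 at an alpha=0.05, yielded an estimated subject size of 19 individuals". The number is raised by one to allow an exploratory look by sex: "That value was inflated to 20 subjects (10 male and 10 female) to permit an exploratory comparison in the primary responses between sexes". Up to 30 people may be recruited, as an allowance for dropout, to reach 20 complete datasets.

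The same paragraph allows the number to change: "interim power analyses will be performed, with the number of required subjects adjusted based upon the variance of the obtained data". It gives no target power and no sidedness for that step.

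On direction, section 2.a sets out to "test the hypothesis that intranasal cocaine impairs core temperature responses during mild to moderate intensity exercise". The data analysis paragraph of section 4.a says only that "we will compare thermoregulatory and cardiovascular data (e.g., baseline and end-exercise") between the two trials, and refers to an earlier passive-heating study for the method. One-sided or one-tailed testing is mentioned nowhere.

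**The concern.** An alpha of 0.05 with no qualifier is normally read as two-sided, and on that reading the stated power cannot be obtained from the stated inputs. Two things are at stake.

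- **The chance of an answer.** A reader takes from the plan a 0.19 chance of missing the projected effect. With a two-sided p-value or 95% confidence interval and 20 completers, the chance is 0.28.
- **Freedom of choice after the fact.** While sidedness is open, there is a band of results that is significant under one choice and not under the other. The interim re-estimate of the sample size has the same ambiguity.

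**Working it through.** **Inputs, all from the sample size paragraph of section 4.a.** Paired t-test; standardised paired difference dz = 0.60; alpha = 0.05; n = 19, raised to 20; mean difference 1.02 − 0.82 = 0.20 °C. The implied SD of paired differences is 0.20 / 0.60 = 0.333 °C.

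**Formula.** Under the alternative, the paired t statistic follows a noncentral t distribution with df = n − 1 and noncentrality dz × √n. One-sided power is the probability that it exceeds the 95th percentile of t. Two-sided power is the probability that its absolute value exceeds the 97.5th percentile.

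**Step 1: the plan's own figure.** At n = 19 the noncentrality is 0.60 × √19 = 2.615 with 18 df. The one-sided critical value is 1.734 and power is 0.808, which rounds to the stated 0.81. At n = 18 it is 0.787, so 19 is the smallest n that reaches 0.80. The plan's number is therefore a correct one-sided result.

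**Step 2: the same inputs, two-sided.** At n = 19 the critical value is 2.101.

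| n | One-sided 0.05 | Two-sided 0.05 |
|---|---|---|
| 18 | 0.787 | 0.670 |
| 19 | 0.808 | 0.696 |
| 20 | 0.827 | 0.721 |
| 23 | 0.873 | 0.785 |
| 24 | 0.886 | 0.804 |

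A simulation of 400,000 runs agrees: at n = 19, 0.809 one-sided and 0.697 two-sided; at n = 20, 0.827 and 0.722; at n = 24, 0.804 two-sided.

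**Step 3: can rounding or an approximation explain the gap?** Taking dz anywhere from 0.595 to 0.605 moves two-sided power at n = 19 only between 0.689 and 0.704. The two-sided normal approximation gives 0.744. Two-sided power of 0.81 at n = 19 would need dz of about 0.69. None of these fits the plan.

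**Step 4: what it means with 20 completers.**
- Chance of missing 0.20 °C: 1 − 0.721 = 0.28 two-sided, against 1 − 0.81 = 0.19 from the stated power.
- Difference detectable with power 0.80: two-sided 0.660 × 0.333 = 0.220 °C; one-sided 0.577 × 0.333 = 0.192 °C.
- Smallest significant observed difference (19 df): one-sided 1.729 × 0.333 / √20 = 0.129 °C; two-sided 2.093 × 0.333 / √20 = 0.156 °C. A result between the two depends on the choice of side. If the planned effect is true, the probability of landing there is about 0.827 − 0.721 = 0.11.

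**Step 5: the interim re-estimate.** Completers needed for a 0.20 °C difference, with an assumed target power of 0.80:

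| SD of paired differences (°C) | One-sided | Two-sided |
|---|---|---|
| 0.30 (assumed) | 16 | 20 |
| 0.333 (from the plan) | 19 | 24 |
| 0.36 (assumed) | 22 | 28 |

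The same observed variance thus leads to different required numbers.

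**The case against.** The strongest reply is that the plan is directional throughout: it expects cocaine to impair heat regulation and projects a larger temperature rise, and 19 is exactly the one-sided answer. On this view only a label is missing, and the lower figures apply only if a two-sided test is read into the text. It stands that there is no arithmetic error and that the one-sided reading is coherent. But a directional expectation does not declare a one-sided test, since such hypotheses are routinely tested two-sided, and the analysis paragraph speaks only of a comparison.

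The cited earlier study might settle the matter. It is not available here, so the claim is limited to these documents. The test behind this trial's sample size should in any case be stated in this trial's plan.

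The plan also has some slack. Two-sided power would be 0.888 if all 30 recruits completed, and 24 completers fit under that ceiling if no more than 6 are lost. Yet the 30 is a dropout allowance and the goal remains 20. The interim analyses could raise the number, but without a stated side or target they cannot be relied on to do so.

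Finally, the effect size carries an uncertainty of similar weight. With SDs of 0.36 and 0.40 °C, dz = 0.60 implies a within-person correlation of (0.36² + 0.40² − 0.333²) / (2 × 0.36 × 0.40) = 0.62, which the plan does not state. At an assumed 0.5, power at n = 19 falls to 0.71 one-sided and 0.58 two-sided. This stands. It is a reason to state the assumed SD of differences beside any power figure, not a reason to leave the sidedness open.

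**Conclusion.** The concern holds, and it should be fixed. The power statement is correct for an undeclared one-sided test and overstated for a two-sided one: by about 0.11 at 19 participants (0.81 against 0.70), and by 0.09 if the stated 0.81 is set against the 0.72 that 20 completers give two-sided. Reaching 0.80 two-sided takes 24 completers, 5 more than one-sided. These figures rest on the plan's dz of 0.60, that is, an SD of paired differences of about 0.33 °C. The loss of power applies if the result is reported two-sided and the number stays at 20. The omission does not invalidate the trial, but it affects how the main result is read and what the interim re-estimate would require.

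**What to change.** In section 4.a, keep 20 completers and declare the primary paired comparison of the core temperature rise as two-sided at 0.05. Replace the power sentence with: power is 0.72 with 20 completers (0.70 with 19), assuming dz = 0.60, i.e. an SD of paired differences of about 0.33 °C. State that the interim power analyses use the same sidedness, and give their target power.

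If a one-sided test was really intended, the alternative is to declare it as the primary test before any data are seen, keep 0.81 (0.83 with 20), and apply it at the interim as well.

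The cost is one or two sentences, with no change to design or conduct. The two-sided route shows a less favourable power and may lead the interim step to ask for more completers (24 against 19 at the planned SD, for a target of 0.80). The one-sided route commits the trial to one direction in advance.

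### The interim rule resets N from the observed variance with no minimum; re-run with the paired SD and free to go below 20, it takes overall type I error to about 0.053–0.063

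*Combined protocol and SAP*

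**What the plan says.** The sample size paragraph of section 4.a projects core temperature rises of 0.82 ± 0.36 °C on placebo and 1.02 ± 0.40 °C on cocaine. It uses the G*Power option for "Difference between two dependent means (matched pairs") and reports: "These predictions resulted in an effect size of 0.60". The result is: "With a study power=0.81 at an alpha=0.05, yielded an estimated subject size of 19 individuals". It then adds one subject: "That value was inflated to 20 subjects (10 male and 10 female) to permit an exploratory comparison in the primary responses between sexes".

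On numbers overall: "Up to 30 participants are anticipated to enroll in this study, with a goal of obtaining complete datasets on 20 individuals". The paragraph closes by calling its planning values estimates, and says that for this reason "interim power analyses will be performed, with the number of required subjects adjusted based upon the variance of the obtained data".

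The plan does not give the number or timing of looks, the variance to be used, a lower limit on N, whether N may fall, or any allowance in alpha. The 20 is a goal and the 30 is a recruitment ceiling; neither limits a downward adjustment. The data analysis paragraph of section 4.a adds "All data will be analyzed while blind to condition and with proper covariate analyses", without linking this to the interim variance. Section 3 sets out the crossover: "eligible participants will be randomized to complete the cocaine or the placebo (lidocaine) trial first".

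**The concern.** If N is recalculated from the variance of the quantity being tested, the final sample size depends on the final test statistic. A small interim SD gives a small N, and few later observations are added to correct that SD. A large interim SD leads to more data and is diluted. Trials that stop early therefore carry an SD that is too small and a t statistic that is too large. With no minimum N, nothing limits this.

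The paired SD is the likely input, because the only calculation named is the matched-pairs one. Masking the condition labels does not help: the SD of A minus B is the same whichever letter is cocaine. At stake is whether the stated alpha of 0.05 is the alpha actually delivered. The rule may well be used, since the plan says the interim analyses will be done and that its inputs, taken from burn survivors, are estimates.

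**Working it through.** **Inputs from section 4.a.** Target difference 1.02 − 0.82 = 0.20 °C; effect size 0.60; alpha 0.05; power 0.81; 19 subjects raised to 20; up to 30 enrolled.

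**Implied paired SD.** 0.20 / 0.60 = 0.333 °C. The implied within-subject correlation is (0.36² + 0.40² − 0.333²) / (2 × 0.36 × 0.40) = (0.1296 + 0.1600 − 0.1111) / 0.288 = 0.62. The plan states neither figure.

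**Reproducing the plan's figure.** Noncentral-t power, with n − 1 degrees of freedom and noncentrality 0.60 × √n, is 0.808 one-sided at n = 19 and 0.696 two-sided. The stated 19 at 0.81 therefore reproduces as a one-sided test. Both versions are shown below because the plan does not state sidedness. The smallest n with at least 80% power is 19 one-sided and 24 two-sided, so 80% is used as the re-estimation target.

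**Assumptions the plan does not supply.** One look at 10, 12 or 15 completers; maximum of 20, 24 or 30 completers; final analysis an unadjusted paired t-test at 0.05; normal differences with true SD 0.333 and no treatment effect.

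**Simulated rule.** Take the SD at the look, find the smallest N giving 80% power for 0.20 °C, clip it to [look size or floor, maximum], and run the t-test. With 300,000–400,000 trials per scenario the Monte Carlo error is about 0.0004. Independent runs agreed to within about 0.001.

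| Interim variance and limits | One-sided | Two-sided |
|---|---|---|
| Paired SD, no floor, maximum 20 | 0.053–0.059 | 0.054–0.060 |
| Paired SD, no floor, maximum 24 or 30 | 0.054–0.060 | 0.056–0.063 |
| Paired SD, floor 20, maximum 24 or 30 | 0.051–0.052 | 0.052–0.054 |
| Treatment-masked SD, with or without floor | 0.049–0.051 | 0.049–0.051 |

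With floor and maximum both at 20 the design is fixed and the error is 0.050.

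**Where the excess sits.** With the paired SD and no floor, N ends below 20 in 57–58% of one-sided and 31–37% of two-sided trials. Within those trials the null rejection rate is 0.070–0.078 one-sided and about 0.10 two-sided. Trials ending at 20 or more run at 0.029–0.040. For a one-sided look at 10 with maximum 30, the share below 20 is 0.58 and its error 0.0762. It contributes 0.58 × 0.0762 = 0.0442 of the overall 0.0595, leaving (0.0595 − 0.0442) / 0.42 = 0.036 for the rest.

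**Sensitivity (paired SD, no floor, maximum 30).**
- True SD 0.25–0.45, look at 8–15: about 0.051–0.065.
- True SD 0.20, look at 10 or later: 0.050–0.052.
- Look at 5 or 6: about 0.058–0.076.
- Repeated looks, which the plural in the plan permits: 0.054–0.065 starting from 10, 0.063–0.078 starting from 5.
- Updating only the two condition SDs, with the correlation fixed at 0.62: 0.051–0.053.

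**The case against.** The strongest reply is that the plan never commits to the version that does harm. It reports condition SDs of 0.36 and 0.40, not a paired SD, and updating those alone with the correlation fixed leaves almost no excess. The final test is also assumed, because the data analysis paragraph defers to an earlier paper and mentions covariates. And a cut below 20 would defeat the stated reason for choosing 20, the comparison of 10 men with 10 women.

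All of this stands, and it makes the point conditional. It does not remove it: the paired calculation is the one named, and nothing in the text rules out the paired SD or a reduction.

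Three stronger readings are tempting and not supported.
- A reader might infer that the planned trial has an inflated error rate. The documents leave the estimator and limits open, and some permitted versions hold 0.05.
- A reader might take 0.053–0.063 as the error once N has fallen below 20, or take 0.10 as the error of the trial. The first is the overall error of a design that allows the fall; the second applies only to trials that end there.
- A reader might infer that a floor of 20 removes the excess entirely. With the paired SD and room to go up to 30, as much as 0.4 points remains.

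**Conclusion.** The concern holds as a conditional and modest one. If the named calculation is repeated with the paired SD and N may fall below 20, overall type I error exceeds the stated 0.05 by about 0.3 to 1.3 percentage points. That range rests on one look at 10–15 completers, a true paired SD of 0.333 °C, a maximum of 20–30 completers and a final unadjusted paired t-test. Very early or repeated looks can take it to about 0.078; a later look with a small true SD brings it back to about 0.05.

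This goes beyond missing detail, since the plan's own rule applied in its most direct way does not keep its own alpha. It is worth changing because the remedy is cheap and should be in place before any interim look; afterwards, the choice of rule cannot be shown to be independent of the data. The sidedness of the power calculation is a separate point.

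**What to change.** Replace the interim sentence with a rule stating that:
1. There will be one re-estimation, at a named number of completers.
2. N may not be reduced below the planned 20 completers. This alone cuts the error to about 0.050–0.054.
3. The 0.20 °C target stays fixed. The variance is the SD of visit 2 minus visit 1 differences, pooled over treatment sequence with sequence masked, and no treatment means or p-values are viewed. This brings the error to about 0.05.
4. The maximum number of completers is named. Recruiting 30 to complete 20 allows for a loss of (30 − 20) / 30, one-third. If that loss is expected, the maximum is 20 and the re-estimation cannot raise N; the plan should then say so, raise enrolment, or drop the re-estimation.

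**Cost.** Wording only, unless enrolment is raised. The option to stop below 20 is lost, which matters little given the target of 10 men and 10 women. A real 0.20 °C effect raises the pooled SD from 0.333 to √(0.1111 + 0.04) = 0.389, so the plan should say whether it is used as it is or with 0.04 subtracted from the variance. The power gain is small: with a look at 12, a maximum of 24 and no subtraction, power at SD 0.333 is 0.85 one-sided or 0.78 two-sided, against 0.83 or 0.72 for a fixed 20. Because this SD does not register a general shift between visits, visit order should be a term in the final model.

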		
4.d. List ALL other research procedures or components not listed in table 4.b.
 
The combination of Tables 4b and 4d should account for all of the research procedures that will take place during this study.
 
Consider grouping similar procedures under a single component (e.g., blood work, CT = safety assessments)
		
#	Research component 
individual procedures example: Eligibility Assessments 
History and physicalQuestionnaireLaboratory tests Add or delete rows as needed	Column A Local Standard Practice Indicate the number of times each procedure will be performed as stipulated in the research plan that would be performed if the participant were not participating in the study.	Column B Research Only Indicate the number of times each procedure will be performed solely for research purposes (meaning that the participant would not undergo the same number of procedures or would not undergo the procedure(s) at the same frequency if they were not participating in the study)	Column D Risks If you are requesting a Waiver of Informed Consent, complete the table below. List the reasonably expected risks for each procedure or group of procedures under the following categories as appropriate: 
• Serious and likely;• Serious and less likely;• Serious and rare;• Not serious and likely;• Not serious and less likely
1	Eligibility assessments			
	Health history assessment	0	Once	
	Body height and mass	0	Once	
	Heart rate and rhythm via 12-lead ECG	0	Once	
	Brachial blood pressure	0	Approximately 3 times	
	Submaximal exercise	0	Once during the screening visit	
	Physical activity questionnaire (IPAQ)	0	Once	
2	Other assessments			
	Core temperatures	0	Continuously during the experimental visits	
	Skin temperatures	0	Continuously during the experimental visits	
	Regional sweat rate	0	Continuously during the experimental visits	
	Whole-body sweat rate	0	Once per experimental visit	

Form A

STU-2023-0094

	Skin blood flow	0	Continuously during the experimental visits	
	Limb blood flow (Doppler ultrasound)	0	Approximately 3 times	
	60 minute of exercise in warm environmental conditions	0	Once per experimental visit	
	Assessments of perceived exertion and thermal perception	0	Approximately every 10 minutes during exercise	
3	Blood sampling			

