less than 10 bpm, both relative to the placebo (lidocaine) trial. Thus, we do not expect blood pressures or heart rates to be excessively elevated. Importantly, in the healthy cohort that will be assessed, such increases in arterial blood pressure and heart rate are inconsequential. Importantly, we will monitor the patient's vital signs continuously for both the cocaine and lidocaine experimental limbs. A physician licensed to prescribe schedule II drugs ([name] DO, [name] MD, or [name] MD) will be present whenever cocaine is administered to observe and intervene should the patient exhibit the slightest evidence of distress. Standard "crash cart" equipment (inclusive of a defibrillator) will always be readily available. As mentioned above, we performed similar trials, using cocaine and lidocaine (PMID: 12044126) in young healthy adults without any complications.

Upon the conclusion of the protocol, subjects will not be permitted to leave the laboratory until all of the following discharge variables are met:

- The subject presents with an Aldrete score (post-anesthesia discharge scoring system) matching baseline,
- The subject demonstrates an awareness of time, person, and place and is able to answer questions appropriately
- The subject is able to stand up and walk for 5 minutes without assistance (supervised)
- The subject is able to drink water and eat crackers without reports of nausea
- The subject able to void

Sub-maximal exercise in thermoneutral conditions: There are no additional risks involved with performing a sub-maximal exercise test beyond that associated with light to moderate-intensity physical exertion. Every precaution will be taken to minimize the risk by closely monitoring vital signs (blood pressure, heart rate and rhythm) throughout the exercise. This test will be stopped if signs or symptoms of cardiac ischemia develop, if excessive hypertension or hypotension develop, or if arrhythmias occur during exercise. A research nurse will be present during the sub-maximal exercise test to interpret any danger signs and symptoms.

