When the participant is undergoing any testing, they will be supervised by an ACLS trained nurse and/or physician. In addition, physicians and nurses at the Institute for Exercise and Environmental Medicine will assist as needed. A physician licensed to prescribe schedule II drugs ([name] DO, [name] MD, or [name] MD) will be present when cocaine is administered. There is a fully stocked "crash cart" with a defibrillator and medications within 50 feet of the laboratory. Anti-arrhythmic medications are rapidly available if a sustained but not life-threatening arrhythmia were to occur. Airway management equipment is also stocked in that cart. Furthermore, the Texas Health Resource Emergency Room is minutes away if an escalation of care is required.

Upon screening, participants will be given contact information for a nurse to contact in case any adverse event occurs following discharge from experimental days. However, this is unlikely to occur given the short-acting effects of cocaine and the fact that participants are not discharged until vital signs are similar to that of baseline values.

c. Will the safeguards be different between/among groups?

Yes

No

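### Does requiring a physician when cocaine is given, with no matching rule for lidocaine, break the double blind?

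*Combined protocol and SAP*

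**What the plan says.** Section 3 sets the design: "We will conduct a double-blind, placebo-controlled, crossover study". Each participant receives both agents, one per visit in randomised order, with lidocaine as the placebo.

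Section 4.a says who gives the agent: a physician with a schedule II licence, "or a research nurse (with oversight from that physician) will administer cocaine (no higher than 3 mg/kg body mass) or placebo". The sentence covers both agents and extends to each experimental visit. It does not say whether oversight means physical presence.

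Section 5.a, under cocaine and lidocaine administration, adds that such a physician "will be present whenever cocaine is administered to observe and intervene should the patient exhibit the slightest evidence of distress". The sentence just before it applies continuous vital-sign monitoring expressly to both agents. Section 5.b says that during any testing "they will be supervised by an ACLS trained nurse and/or physician", and again that the licensed physician "will be present when cocaine is administered". Neither section states physician presence for lidocaine.

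No section says who prepares the agents, who holds the code or who arranges the physician's attendance. Item 5.c asks about differing safeguards, but its answer cannot be read in the available text and is given no weight here.

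**The concern.** The staffing rules are symmetric except in one respect. A physician, or a nurse under that physician's oversight, may give either agent, and a nurse may supervise testing alone. Presence at administration is written for cocaine only. Someone who knows that rule and sees the agent given with no physician present could conclude that it is lidocaine, and that the other visit is cocaine.

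The exposed measures would be those open to expectation. Section 4.d lists "Assessments of perceived exertion and thermal perception" about every 10 minutes during exercise, and section 5.a has a research nurse stop exercise on signs or symptoms. The sample size in section 4.a rests on the rise in core temperature over 60 minutes of exercise, so unequal early stopping could reach that comparison indirectly. Analysing the data blind to condition, as section 4.a promises, would not repair ratings given or decisions taken at the visit.

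**Working it through.** The plan states no figure on this point, so the check is mainly a comparison of texts.

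**Step 1. Which combinations comply?**

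| Physician at administration | Agent | Section 4.a (at least oversight) | Sections 5.a and 5.b (presence for cocaine) |
|---|---|---|---|
| Present | Cocaine | met | met |
| Present | Lidocaine | met | not applicable |
| Absent, oversight in place | Cocaine | met if oversight does not require presence | breached |
| Absent, oversight in place | Lidocaine | met if oversight does not require presence | not applicable |

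The asymmetry is real but lies only in the last two rows. It disappears if oversight in section 4.a was meant as presence. The first two rows satisfy every passage, so nothing contradicts.

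**Step 2. What can blinded staff do?** Take double-blind in its usual sense: the participant and the staff running the visit do not know the agent. Either visit may then be the cocaine visit. The only way to be certain a physician is there for cocaine is to have one at both administrations. That puts every visit in the first two rows and removes the cue. The last row can occur by design only if someone who knows the allocation decides when a physician attends, and keeps to the minimum.

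**Step 3. How large would the cue be in that case?** Assumptions, none of them given in the documents:

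- The order is allocated 1:1.
- A physician is always present for cocaine.
- A physician is absent at a share p of lidocaine administrations.
- The observer knows the rule.

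From the documents: 20 complete datasets, 60 minutes of exercise, ratings about every 10 minutes (60/10 = about 6 per visit).

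- Participants with both visits identified: 20p. This is 0 at p = 0, 5 at p = 0.25, 10 at p = 0.5 and 20 at p = 1.
- Share of allocations guessed correctly, tossing a coin when there is no cue: p + 0.5(1 − p) = 0.5 + 0.5p. This is 50%, 62.5%, 75% and 100%.
- Probability of cocaine, given a physician present at a single visit: 0.5/[0.5 + 0.5(1 − p)] = 1/(2 − p). This is 0.50, 0.57, 0.67 and 1.00.

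Order matters for the ratings. If lidocaine comes first (10 participants), a physician's absence precedes the ratings of both visits. If cocaine comes first (10 participants), it precedes only those of the second. For p below 1, the visits rated after certainty number 10p × 2 + 10p × 1 = 30p, or about 30p × 6 = 180p rating times: 0 at p = 0, 45 at p = 0.25 and 90 at p = 0.5.

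Every one of these results except the baseline at p = 0 restates the unknown p. None of them is evidence that p exceeds zero.

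**Step 4. What does the rule attach to?** It attaches to giving the drug and watching for distress then. Section 5.a assigns monitoring during exercise to a research nurse without distinguishing agents, so a nurse alone with the participant during exercise reveals nothing.

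**The case for a change.** The best case for a change is that the document names both agents where it means both: vital-sign monitoring is stated for both, and physician presence in the very next sentence is not. It never says who is unblinded, although someone must know the agent in order to prepare it. If attendance is in fact the same at both visits, one sentence would settle the matter, and blinding lost at a visit cannot be recovered.

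Part of this stands. The wording is asymmetric, and the documents do not identify any unblinded role. But sections 5.a and 5.b answer form questions about reducing risk and handling adverse events. Stating a minimum safeguard for one agent there does not say that the physician stays away for the other. Someone who knows the agent in order to prepare it need not be the person who schedules physicians. The harm also requires an observer who knows the rule, and no section says participants are told it. A clarifying sentence would do no harm, but its absence does not make the plan wrong. Going further, to require equal attendance while keeping the cocaine safeguard, would in effect write a supervision rule for lidocaine, and that is a clinical matter on which this note takes no view.

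**Conclusion.** No change to the plan follows. The written rule for physician presence covers cocaine administration only, but it is compatible with the double blind, and blinded staff can be sure of following it only in a way that leaves no cue. The remaining gap is an unstated operational detail.

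The possible size runs from 0 to 20 of the 20 targeted datasets, according to an attendance share on which the documents are silent. Any resulting bias in ratings or stopping cannot be computed. Core temperature is read by an ingested or rectal sensor and the 39.5 °C stopping limit is objective, so the comparison that drives the sample size is exposed only through symptom-based stopping.

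This rests on two assumptions: that double-blind has its usual meaning for the staff running the visits, and that nobody with knowledge of the allocation schedules physicians to the written minimum. If the second proved false in practice, the blind at administration would need a fresh look.
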